### **Secondary outcomes**

Secondary outcomes are verified SARS-CoV-2 infection (first event), self-reported respiratory infection, and all-cause hospitalization (first event). Information on positive test results will be retrieved from the Danish Health Data Authority (Sundhedsdatastyrelsen) and information on self-reported respiratory infections will come from the follow-up questionnaires.

Verified SARS-CoV-2 infection is defined as having a positive SARS-CoV-2 PCR (Polymerase Chain Reaction), rapid antigen test, or converting from negative to positive antibody test (IgG positive) without having been vaccinated.

Self-reported illness is defined as a respiratory infection if the participants report having had a respiratory infection such as common cold, influenza, pneumonia or similar term, or they report having had one or more of the following symptoms: cough, sore throat, runny nose/nasal congestion (common cold symptoms), loss of smell or taste sense, or dyspnea with or without general symptoms such as fever, chills, muscle ache, headache, and fatigue (dyspnea only if in combination with fever).

All-case hospitalization (first event) will include all hospital contacts with duration of 24 h or more, to ensure we only include hospital admissions and not visits to outpatient clinics.

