## Variables

Variable	Definition	Type	Scale
Primary outcome:			
Acute infection	Death, hospitalization, antibiotic treatment, or visit to GP due to newly onset infectious disease. Composite outcome.	Categorical, binary	0,1
Death due to infection	Death due to infectious disease.	Categorical, binary	0,1
Hospitalization for infection	Hospital contact due to infectious disease.	Categorical, binary	0,1
Antibiotic treatment	Antibiotic treatment during follow-up.	Categorical, binary	0,1
Doctor diagnosed infection	Infection identified by GP or on-call doctor.	Categorical, binary	0,1
Secondary outcomes:			
Self-reported respiratory infection	Reported respiratory symptoms or disease compatible with respiratory infection.	Categorical, binary	0,1
Verified CoV  infection (first event)	Positive SARS-CoV-2 test.	Categorical, binary	0,1
All-cause hospitalization	Admission to hospital > 24 hours (first event).	Categorical. binary	0, 1

 SARS-CoV-2 infection.

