#### **Supplementary analyses**

We will conduct preplanned supplementary analyses to assess possible effect modification by other vaccines given during follow-up, previous BCG vaccination, and COVID-19 vaccination before inclusion. These will be done using the same methods as described above for the primary (composite) outcome and for all secondary outcomes.

1. Before and after receipt of subsequent vaccines, and adjusted by type of subsequent vaccine, to assess possible interaction between BCG and other vaccines. Vaccination status will be categorized as 1) No other vaccines, 2) COVID 19 vaccine, 3) Influenza vaccine, or 4) COVID 19 and influenza vaccine.

Vaccination status will be included as a time varying covariate changing on the date of vaccination with subsequent vaccines received during follow-up. Some participants received a pneumococcal vaccine (23-valent polysaccharide vaccine) together with their influenza vaccine as was recommended by the Danish Board of Health in 2020. We will therefore include influenza vaccines with or without concurrent pneumococcal vaccination (given on the same day). Participants will be censored upon receipt of any other vaccines than the above mentioned.

2. By previous BCG vaccination (Yes/no, self-reported and assessed by BCG scar) to assess the effect of revaccination vs. first vaccination with BCG.

3. By COVID-19 vaccination status at inclusion (Received COVID 19 vaccines yes/no).

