### Exploratory analysis

Participants were enrolled during different stages of the COVID-19 pandemic. We will therefore conduct a subgroup analysis of all outcomes comparing participants included in the same phase of the pandemic. We will compare outcomes for participants included in the following periods:

1. September 2020 to January 2021 (N=1239); before the COVID-19 vaccines were widely distributed to the target population. A period characterized by increasing infection control measurements and concluding in lockdown.
2. April to December 2021 (N=438); Participants are now being vaccinated with the new coronavirus vaccines; most have had the two or three doses before enrollment. A period characterized by varying COVID-19 activity; a minimum of restrictions on society despite periodically high transmission rates (Omicron variant in the fall).

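### The Table 3 rows by COVID-19 vaccination for verified SARS-CoV-2 infection do not count the same events, because IgG seroconversion counts only in unvaccinated people

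*SAP*

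**What the plan says.** All places are in SAP Part A.

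- **Section 6.0, Secondary outcomes.** Verified SARS-CoV-2 infection (first event) has three routes. Two are open to every participant: "having a positive SARS-CoV-2 PCR (Polymerase Chain Reaction), rapid antigen test". The third is "converting from negative to positive antibody test (IgG positive) without having been vaccinated".
- **Section 6.0, Variables table.** The outcome appears only as "Positive SARS-CoV-2 test", without the vaccination restriction.
- **Section 7.0, Supplementary analyses.** The purpose is "to assess possible effect modification by other vaccines given during follow-up, previous BCG vaccination, and COVID-19 vaccination before inclusion", and the analyses are run "for the primary (composite) outcome and for all secondary outcomes". Two of them involve COVID-19 vaccination. One is "Before and after receipt of subsequent vaccines, and adjusted by type of subsequent vaccine, to assess possible interaction between BCG and other vaccines", with a status that switches on the day of vaccination. The other is "By COVID-19 vaccination status at inclusion (Received COVID 19 vaccines yes/no".
- **Table 3.** Each of these comparisons has its own rows under *Verified COVID-19*, with a hazard ratio and an absolute risk reduction per row.
- **Section 7.0, Secondary outcomes.** The outcome goes into a standard Cox model. Questionnaire episodes get a dating rule; an IgG conversion gets none.
- **Section 7.0, Exploratory analysis.** Results are also shown for two enrolment periods. In the second, "most have had the two or three doses before enrollment".

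The SAP plans no PCR/antigen-only version of this outcome.

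**The concern.** The supplementary analyses ask whether COVID-19 vaccination changes the effect of BCG. That question is answered by comparing rows, and rows can be compared only if they count the same event. Here they do not. In unvaccinated people an infection that was never tested can still count through serology. In vaccinated people it cannot. A difference between rows may then reflect the definition and be read as an interaction between BCG and the COVID-19 vaccine.

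The dating gap adds to this. A seroconversion is known only to lie between two blood samples, but the time-varying analysis needs each event on one side of the vaccination date.

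**Working it through.** The SAP states no rate, effect or detection share for this outcome, so there is no figure of the plan to reproduce. The Part A sample size of 1890 concerns the primary outcome and does not enter.

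**1. Which route is open in which row.** I read the restriction as meaning COVID-19 vaccinated; the SAP does not say so, nor when status is judged.

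| Table 3 row, *Verified COVID-19* | PCR/antigen | IgG conversion |
|---|---|---|
| COVID-19 vaccinated before enrolment: yes | open | closed |
| COVID-19 vaccinated before enrolment: no | open | open until a COVID-19 vaccine is given in follow-up |
| Before other vaccines | open | open only if not COVID-19 vaccinated at enrolment |
| After other vaccines: influenza only | open | open only if not COVID-19 vaccinated at enrolment |
| After other vaccines: COVID-19, or both | open | closed |
| After other vaccines, all types together | open | mixed |

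**2. Absolute risk reduction.** All inputs are assumptions: true placebo risk r = 5–20%; true risk ratio 0.75 in both strata (no interaction); share t = 0.5–0.9 of infections found by PCR/antigen in both strata; share g = 0.3–0.9 of the missed infections found by serology, in the unvaccinated only.

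- Vaccinated: ARR = r × t × (1 − 0.75)
- Unvaccinated: ARR = r × [t + (1 − t)g] × (1 − 0.75)

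| r | t | g | Vaccinated | Unvaccinated |
|---|---|---|---|---|
| 10% | 0.5 | 0.6 | 0.10 × 0.50 × 0.25 = 1.25% | 0.10 × 0.80 × 0.25 = 2.00% |
| 20% | 0.5 | 0.9 | 0.20 × 0.50 × 0.25 = 2.50% | 0.20 × 0.95 × 0.25 = 4.75% |
| 10% | 0.9 | 0.3 | 0.10 × 0.90 × 0.25 = 2.25% | 0.10 × 0.93 × 0.25 = 2.33% |

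The second line is the largest gap in the range examined. The third shows how small the gap becomes when PCR/antigen finds most infections.

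**3. Relative effect** (risk ratio, standing in for the hazard ratio).

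- *No false positives, BCG acting equally on infections found by either route:* the detection share cancels and the ratio is 0.75 in both strata. There is no artefact.
- *False-positive seroconversion with probability f, unvaccinated only.* With u = t + (1 − t)g, the ratio is [0.75ru + (1 − 0.75ru)f] / [ru + (1 − ru)f]. For r = 10%, t = 0.5, g = 0.6, f = 1%: (0.0600 + 0.0094) / (0.0800 + 0.0092) = 0.0694 / 0.0892 = 0.78. Over the full range it is 0.76–0.81 for f = 1% and 0.77–0.85 for f = 2%, against 0.75 in the vaccinated.
- *BCG prevents test-detected infections but not those found only by serology.* The ratio is [0.75t + (1 − t)g] / [t + (1 − t)g]. For t = 0.5, g = 0.6: (0.375 + 0.300) / 0.800 = 0.84. The range is 0.76–0.87, against 0.75.

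**4. With one definition.** Using PCR/antigen only in both strata, the first line of the table in step 2 gives 1.25% and 1.25%, with a ratio of 0.75 in each. The definitional difference is gone.

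**The case against.** The restriction is sensible: COVID-19 vaccination can itself turn IgG positive, so counting conversions after vaccination would create false infections. Within each stratum at inclusion both arms share one definition, so those randomised contrasts are valid. The IgG route can also close during follow-up for people who were unvaccinated at inclusion, which dilutes the difference between those rows. All of this stands.

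The strongest objection concerns the remedy. Suppose BCG prevents no infections but lowers test detection by 25%, for example through milder symptoms. The true infection ratio is then 1.0. With t the test-detected share under placebo, the three-route definition in the unvaccinated gives [0.75t + g(1 − 0.75t)] / [t + g(1 − t)]. That is 0.80 / 0.90 = 0.89 for t = 0.8, g = 0.5, and 0.86 / 0.88 = 0.98 for t = 0.4, g = 0.8. PCR/antigen only gives 0.75 in both strata: they agree, but further from the effect on infection. This stands too. The common definition should therefore be added beside the three-route one, not replace it, and be labelled as an effect on test-detected infection.

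A reader might infer that the definition is bound to produce a false hazard-ratio interaction. It is not: step 3 shows that this needs a further assumption. Section 2.0 does allow that BCG may act on severity as well as on infection, but the SAP gives no figure for either. A reader might also infer that the enrolment-period comparison fails for the same reason. That analysis is labelled exploratory, looks at participants within the same pandemic phase, and names restrictions, transmission and Omicron beside vaccination.

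The blood-sampling schedule may well be in the protocol, so its absence is no fault. The convention for dating an event in the Cox model belongs in the SAP.

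**Conclusion.** The point holds in a limited form. The Table 3 rows for verified SARS-CoV-2 infection by COVID-19 vaccination count different events. The absolute risk reductions are therefore not comparable across rows even when BCG works equally well in each. The hazard ratios are comparable only if serology has no false positives and BCG acts alike on test-detected and serology-only infections.

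The size cannot be found from the SAP. In the illustrations it runs from practically nothing (2.25% against 2.33%) to about a doubling (2.50% against 4.75%), and it may well be small. These figures assume equal true risk and equal PCR/antigen detection in both strata.

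The Table 2 comparison and the within-stratum contrasts at inclusion remain valid. The point touches supplementary rows of one secondary outcome. It is a cheap improvement, not a threat to the trial's main conclusions.

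**What to change.** - In the Table 3 *Verified COVID-19* rows by COVID-19 vaccination (at inclusion, and before/after and by type where a COVID-19 vaccine is involved), report the BCG effect on PCR- or antigen-positive infection, dated by the test, beside the three-route result.
- Base any statement on interaction between BCG and COVID-19 vaccine on that common definition, and call it an effect on test-detected infection.
- Report serology-only conversions separately by arm. Do not place them as dated events on one side of the vaccination date in the time-varying analysis.
- State that the restriction means COVID-19 vaccinated, when status is judged, and what date a seroconversion receives wherever it stays in a Cox model. Bring the Variables table into line.
- The enrolment-period rows need at most the same PCR/antigen row as a sensitivity result.

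The cost is SAP wording and one derived variable, with no new data. The price is fewer events and wider intervals in the unvaccinated rows, and an endpoint that depends more on symptoms. A common definition also does not ensure equal testing in vaccinated and unvaccinated people, which is a further reason for the label.

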## 3.0 STUDY METHODS

### Trial design

A single-blinded, placebo controlled randomized clinical trial. Participants are randomized 1:1 to BCG or placebo and will be followed for 12 months post-randomization with respect to illness, medical contacts, use of antibiotics, hospitalization, and death. The follow-up takes place both through self-reporting and through the Danish National Registers. The participants will receive an electronic questionnaire biweekly with questions about illness, medical contacts, other vaccinations, and side effects.

People  $\geq 65$  years of age are eligible for participation.

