## 6.0 DESCRIPTION OF OUTCOMES AND VARIABLES

### Primary outcome

The primary outcome is a composite outcome: acute infection identified either by a doctor, by antibiotics use, by hospitalization, or by death due to infection. All subcomponents will also be presented separately.

Information on hospitalizations, deaths, and antibiotics use is retrieved from national health registers: The Danish National Patient Register, The Central Person Register, and The National Prescription Register. All hospital contacts due to acute infection will be included, regardless of duration of the contact. An acute infection event identified by a doctor is defined as newly onset infectious illness that has prompted the participant to seek medical attention from general practitioner (GP) or on-call doctor and is based on self-reporting. Participants are asked in the questionnaires, if they have needed to see their GP or an on-call doctor due to newly onset illness during the past 14 days (yes/no). Thus, participants can only have one such event per survey period (14 days). For all outcomes, a honeymoon period of 14 days will be used to define new events.

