#### **Secondary outcomes:**

The secondary endpoint self-reported respiratory infection will be analyzed the same way as the primary endpoint. As participants are only able to report one infectious episode during a follow-up questionnaire, the event will be assigned to the first day within the questionnaire period, and the following 14 days of follow-up excluded for analyses as it represents risk free time.

The secondary outcomes verified SARS-CoV-2 infection and all-cause hospitalization will be analyzed in a standard Cox proportional hazards model, but otherwise as described above.

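### Part A has no rule that separates a new respiratory infection from one still being reported, so one ongoing complaint reported as illness can count as several infections

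*SAP*

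**What the plan says.** All references are to the SAP, Part A.

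- **Survey interval (section 3.0, Trial design).** "The participants will receive an electronic questionnaire biweekly with questions about illness", over 12 months of follow-up.
- **Definition (section 6.0, Secondary outcomes).** "Self-reported illness is defined as a respiratory infection if the participants report having had a respiratory infection" or at least one listed symptom: "one or more of the following symptoms: cough, sore throat, runny nose/nasal congestion (common cold symptoms", and others. General symptoms such as fever are optional; only dyspnea needs fever alongside it. No onset, duration or change-from-usual condition is given.
- **Contrast (section 6.0, Primary outcome).** The doctor-visit item asks about visits "due to newly onset illness during the past 14 days". The new-onset wording is used there and for the composite in the variables table, but not for self-reported respiratory infection.
- **Gap between events (section 6.0, Primary outcome).** For all outcomes, "a honeymoon period of 14 days will be used to define new events".
- **Dating and exclusion (section 7.0, Secondary outcomes).** "the event will be assigned to the first day within the questionnaire period, and the following 14 days of follow-up excluded for analyses".
- **Model (section 7.0).** "The secondary endpoint self-reported respiratory infection will be analyzed the same way as the primary endpoint", that is, with an Andersen-Gill model for recurrent events.

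No rule links what a participant reports in one survey to what the same participant reported in the previous one.

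**The concern.** The 14-day gap is meant to define what counts as a new event. Because the event is moved back to the first day of its survey window, and the window is itself 14 days long, the gap is used up by the window that produced the event. Nobody has to be free of symptoms before a second infection is counted.

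Two kinds of report are affected, with different consequences:

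- **Standing symptoms unrelated to infection**, such as a long-term cough declared as illness. BCG cannot prevent these. In a recurrent-event model each repeat adds an event with no treatment effect, so the hazard ratio moves towards 1. The baseline table records lung disease and smoking, so such participants may be present, although the SAP does not say how many or how often they would report illness.
- **True infections that run into the next window.** These can be counted more than once, so the hazard ratio reflects how long illness lasts as well as how often it starts.

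**Working it through.** **The plan's own figure.** The SAP gives no rate or effect size for this outcome. The only Part A design figure is 945 per group for the primary outcome (20% against 15%, two-sided 0.05). The normal-approximation formula for two proportions gives 906 per group at 80% power and 945 with continuity correction. Part A does not state its power; 80% is inferred from that match. The figure reproduces and is not touched by this point.

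**How often one complaint can count.** Twelve months holds 365/14 ≈ 26 windows. An event in the first window is dated day 1.

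- If days 1-14 are taken out, day 15 (first day of the next window) is at risk again: up to 26 events a year.
- If the 14 days after day 1 are taken out (days 2-15), day 15 is excluded and the next possible event is on day 29: up to 26/2 = 13 a year.

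An illness of d days touches on average 1 + (d-1)/14 windows: 1 + 6/14 = 1.4 for 7 days and 1 + 13/14 = 1.9 for 14 days. On the first reading these illnesses can count twice. On the second they count once, and a double count needs an illness reaching three windows, at least 1 + 14 + 1 = 16 days.

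**Dilution by standing symptoms, by hand.** Assumptions: true hazard ratio 0.75; 1 true infection a year in other placebo participants; a share c with standing symptoms reported throughout, counted k times a year and unaffected by BCG.

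Share of events from standing symptoms: s = ck / (ck + (1-c)×1). Approximate hazard ratio: 1 - 0.25×(1-s).

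| c | k | s | Hazard ratio |
|---|---|---|---|
| 2% | 13 | 0.26/1.24 = 21% | 0.80 |
| 5% | 13 | 0.65/1.60 = 41% | 0.85 |
| 2% | 26 | 0.52/1.50 = 35% | 0.84 |
| 5% | 26 | 1.30/2.25 = 58% | 0.89 |

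**The same by simulation.** 26 biweekly surveys, 150,000 participants per arm, Andersen-Gill estimate, true hazard ratio 0.75, standing symptoms reported at every survey. With none, the estimate is 0.75.

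| Infections per year | Standing symptoms | Day 15 at risk | Day 15 excluded |
|---|---|---|---|
| 1 | 2% | 0.84 | 0.82 |
| 1 | 5% | 0.90 | 0.84 |
| 1 | 10% | 0.93 | 0.89 |
| 0.5 | 5% | 0.93 | 0.91 |
| 2 | 5% | 0.86 | 0.82 |

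**Continuing true infections only, 1 a year, no standing symptoms.** The chance that an infection is still reported at the next survey was set at 0.2 and 0.4.

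- Equal in both arms: the hazard ratio stays at about 0.75-0.76 on either reading. Events per placebo participant rise from 0.98 to 1.20 and 1.56 with day 15 at risk, and from 0.95 to 0.99 and 1.11 with it excluded.
- 0.4 under placebo and 0.2 under BCG: the hazard ratio is 0.59 with day 15 at risk and 0.66 with it excluded, away from 1.

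**Effect of requiring a symptom-free survey first** (1 infection a year, 5% with standing symptoms).

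- Reported at every survey: 0.76, against 0.90 (day 15 at risk) or 0.84 (excluded).
- Reported at half of surveys: 0.82, against 0.86 or 0.83.
- Illness shortened by BCG, as above but without standing symptoms: 0.755, so the distortion from duration disappears.

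**The case against.** The strongest case on the other side has four parts.

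1. **Not every cough counts.** A reader might infer that any reported cough or runny nose is an infection. The definition classifies illness that the participant has already reported. Part B (section 13.0, Secondary outcomes) describes a question on having been ill before the symptom list. If Part A's questionnaire works the same way, some habitual symptoms never enter. This stands, and it limits the problem to complaints declared as illness. It does not remove the problem, because nothing requires the illness to be new.
2. **The literal gap may block back-to-back events.** Read as days 2-15, the exclusion covers the next window's first day, and a short illness counts once. This is a fair reading, but the text does not settle it, and a persistent complaint can still count every second survey.
3. **Continuing illness need not dilute.** A reader might infer that every repeated count pulls the hazard ratio towards 1. The simulation shows otherwise: with equal duration it is unchanged, and with shorter illness under BCG it moves the other way. Dilution applies only to symptoms that BCG cannot affect.
4. **The size is assumed.** The SAP gives no infection rate, share with standing symptoms or effect size for this outcome, and the 25% reduction belongs to the primary outcome. Lung disease and smoking in the baseline table say nothing about how often those participants report illness. This stands in full. The upper end also needs illness declared at all 26 surveys.

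**Conclusion.** The point holds for this secondary outcome. As written, one ongoing or chronic complaint reported as illness can be analysed as several respiratory infections, up to 26 or up to 13 a year depending on an unstated boundary. Two analysts following the SAP could obtain different event counts from the same data.

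Under the stated assumptions (true hazard ratio 0.75, one infection a year, 2-5% reporting standing symptoms throughout) the estimate becomes about 0.80-0.90. At 5%, infection rates of 0.5 to 2 a year give 0.82-0.93. These figures illustrate what the rule can do; they do not predict this trial's result. For continuing true infections the consequence is inflated counts and a hazard ratio that mixes incidence with duration, with no fixed direction of bias.

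A reader might go further and infer that a few participants will dominate the count, or that the primary analysis is compromised. The documents support neither. The first is reached only at the extreme of the assumed range (58% of events). On the second, the primary outcome's self-reported component has its own new-onset condition, and the sample size does not rest on this outcome.

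**What to change.** In section 7.0, Secondary outcomes, state that a respiratory infection is new only if the immediately preceding survey was completed and reported no respiratory illness. Otherwise treat the report as the same episode and keep that time out of the risk set.

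State also:

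- how a report is handled when the preceding survey was skipped, since section 7.0 (Missing data) counts follow-up only in periods with completed questionnaires;
- whether the first day of the next window is at risk after an event.

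Report the present rule and a first-event analysis as sensitivity analyses.

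The cost is SAP wording and recoding of questionnaire data already collected. True infections in consecutive windows are merged, so some events are lost. With no continuing or standing symptoms, simulated events per placebo participant fall from 0.98 to 0.95 at one infection a year and from 1.93 to 1.79 at two, compared with the reading that puts day 15 at risk. Intermittent chronic symptoms are only partly removed (0.82 instead of 0.86 when reported at half of surveys).
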